Aim (WS4) - Make recommendations on the effectiveness of different digital alerts and the most effective method of implementation using a systems modelling approach to assess causality of effects, including a mediation analysis (WS4)

Objectives

- 4.1. Identify the most effective digital alert for improving outcomes for patients with sepsis
- 4.2. Update our current understanding of QI implementation methodologies, with digital alerts as a specific example.
- 4.3. Identify more challenging aspects of the implementation of digital alerts in order to improve sustainability of digital interventions, if appropriate
- 4.4. Using mediation analysis, establish causal pathways between digital alert interventions and impact, incorporating qualitative and quantitative findings from WS1-3

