The study will collect data on patient outcomes prior to the introduction of the alert for a maximum of five years and up to three years post the duration of the alert. We may have to use shorter time periods for certain Trusts.

Sampling Strategy

We have identified five digitally mature NHS Trusts in England, each operating a digital sepsis alerts. In addition, we are working with a Trust in Wales which is still paper based.

Methods of Data Collection

A detailed data specification and data dictionary will be compiled, with associated SNOMED codes for each observation. All data items are routinely collected and recorded in patient electronic records. All data will be de-identified. We will use the NIHR-HIC data infrastructure to enable data transfer. Please see Section for more details.

Outcomes

The primary outcome will be **all-cause in-hospital mortality within 30 days**. Secondary outcomes (including process measures):

- Transfer to ICU
- Length of stay
- Readmission within 30 days
- Administration of IV antibiotics
- Venous blood tests including lactate and white blood cell count
- Blood cultures ordered

The primary reason for the introduction of EWS systems, including digital alerts, is to prevent avoidable clinical deterioration. Mortality is a key measure of clinical deterioration and the majority of EWS have been validated by assessing their ability to predict mortality. Mortality is recorded in hospital patient records and reported as part of the Secondary Users Service (SUS). It is therefore a reliable and commonly used measure of clinical deterioration. Transfer to ICU is often used as an additional measure of clinical deterioration and is available in EHRs.

Length of stay and readmission within 30 days are important indicators of patient experience and are key targets for hospitals. The aim of early recognition of sepsis is to enable prompt and appropriate treatment. We will therefore assess whether the introduction of digital alerts has impacted on appropriate treatment.

Assessment of unintended consequences

Based on discussion in the Sepsis Big Room clinical teams are concerned about potential increases in unnecessary treatment as an unintended consequence of digital alerting. We will consider four potential measures of unintended consequences:

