For the primary analysis we will identify patient hospital encounters where the alert was active and visible to clinicians and use EHRs to identify a cohort of patients who have the same clinical characteristics as the alerting patients, based on routinely recorded vital signs or alerting software. These will act as a control group. Statistical analysis plans will be dependent on the implementation approach in individual Trusts. In line with the approaches recommended in the MRC guidance, methods to be included are those where the factors which determine the exposure can be measured: matching; regression adjustment; and propensity score approaches. We will also utilise methods which are best suited for adjusting for pre-implementation trends including interrupted time series. All analyses will be adjusted for clustering of patients within wards or Trust sites.

Secondary analysis

We will use a controlled multilevel interrupted time series regression to examine trends in mortality for patients with codes defined as 'suspicion of sepsis' and a more robust definition of sepsis. utilise this method to examine unintended consequences identified above.

Sensitivity analysis

We will consider mortality following an A&E attendance for stroke and/or trauma as an unrelated outcome in a sensitivity analysis. Although these patients may trigger an alert, we would not expect their treatment to be different after the introduction of the alert as they are likely to be identified rapidly on arrival. This will enable an assessment of the specificity of effect. This will be included in primary and secondary analysis. These conditions will be included as controls in controlled interrupted time series.

Study Sequence and Duration

Data extraction will commence in March 2022 and be completed by May 2022. Analysis will be completed by December 2022.

7.3 WorkStream 3 – To explore the views and experiences of healthcare professionals and patients/carers on the use of digital sepsis alert systems in hospitals.

Methodology

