10. ANALYSIS

WS2 – Description of Analytical Methods

Detailed statistical plans are included in Appendix 1.

WS3 - Description of Analytical Methods

Data from interviews, focus groups and field notes from observations will be analysed inductively using thematic analysis.³²⁻³³ Thematic analysis allows the research team to take a pragmatic approach to data collection, remaining grounded in the data but ensuring that the analysis answers the research objectives. NVivo 12 software will be used to assist with the organisation and coding of data. We will support the rigour and trustworthiness of the analysis by triangulating healthcare professional and patient data to get a fuller understanding of how sepsis is managed in hospitals. We will assess the transferability of findings by comparing findings across the several Trusts taking part in the research and will describe the context of each Trust in detail to help establish what is common and different in findings between contexts. Confirmability will be established by making clear records of processes involved in data analysis and ensuring that findings can be tracked back to the original source(s).

To inform analysis we will collect data on healthcare professionals' sex, job role, years of experience in current role, and clinical expertise. We will collect data on patients' and carers' sex, age, nationality and ethnicity.

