Although we would expect digital sepsis alerts to have the main impact on patients with sepsis, and this is the stated aim of many commercial sepsis alerts, administrative data may not be sufficient to identify patients with sepsis, particularly as national guidance on sepsis coding changed in 2014, effectively increasing the number of patients with an official diagnosis of sepsis.[5] In addition, efficient clinical response to digital sepsis alerts may result in a decrease in disease progression to sepsis. We have therefore decided to focus on outcomes of patients with an ICD-10 Suspicion of Sepsis code.[6] We will use interrupted time series with a control to determine the impact of the introduction of alerts on patient outcomes and process measures. Interrupted time series is an important methodology which allows

before and after comparisons whilst taking trends prior to the intervention into account and is considered a robust methodology for analysing natural experiments. However, confounding due to other 'interventions' occurring at the same time as the intervention of interest can confound interpretation. A control is an appropriate method to take this type of confounding into account.[7]

For the control we have selected patients with an ICD-10 code included in the category gastrointestinal bleeding. This is a suitable control as we would not expect these patients to trigger a sepsis alert and outcomes should not be impacted by patients being identified as having sepsis. The ICD-10 codes included in this indicator are shown in Table 1.

Objective - Quantify the impact of a digital alert on the key patient outcomes and process outcomes

Primary outcome: in-hospital mortality within 30 days

Secondary outcome: length of stay

ICU admission

2.Methods

2.1Study design

Setting - Describe the setting, locations, and relevant dates, including periods of recruitment, exposure, follow-up, and data collection

This is a time series analysis across five NHS Trusts in England and one NHS Trust in Wales. The period of study is 1st April 2010 to 31st March 2021.

2.2 Participants - the eligibility criteria, and the sources and methods of selection of participants All adult (18+) inpatients admitted as emergency patients between 01/04/10 and 31/03/2 are initially eligible for inclusion in the study.

Intervention group: patients with a discharge diagnosis including one of the SoS sepsis codes at any place in the diagnosis.

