Length of stay - length of stay, measured in hours, was determined from the date and time of admission and discharge recorded in the patient record. For this descriptive study we will quantify length of stay for patients who are discharged alive.

Mortality – mortality was based on discharge destination recorded. For the purposes of this study only inhospital mortality was available for all NHS trusts.

Missing data

Patient admissions will not be excluded if patient data is missing, an additional category of missing will be included for age, gender, ethnicity and deprivation. As part of quality checks we will confirm whether there are any patterns in missing data.

Statistical methods

(a) Describe all statistical methods, including those used to control for confounding

Descriptive analysis

We will describe trends in patient mix over time using graphical methods, we will use time series to determine if there were changes in patient mix, including sub-groups of patients, patients with SoS and falls patients.

We will use break point approaches to identify potential key points in time where changes occurred. This will aid in interpretation of results.

Comparative analysis

We will use interrupted time series with a control, adjusted for patient case mix and season. Each Trust will be modelled separately as the introduction of sepsis alerts and electronic health records is different for each Trust. Comparisons will be made between the change in slope and step change in counts.

(b) Describe any methods which will be used to examine subgroups and interactions

Within each model we will separately consider subgroups when we perform our analysis. We will consider a priori interactions.

(c) Explain how missing data will addressed

Missing data will be included as a category on its own for factors such as ethnicity and deprivation. We will inspect data to identify periods of missing data, and consider imputation.

ICD-10 Code	ICD-10 Description
1850	Oesophageal varices with bleeding
K226	Gastro-oesophageal laceration - haemorrhage syndrome K228 Other specified diseases of oesophagus
K250	Gastric ulcer, acute with haemorrhage
K252	Gastric ulcer, acute with both haemorrhage and perforation
K254	Gastric ulcer, chronic or unspecified with haemorrhage K256 Chronic or unspecified Gastric ulcer with both haemorrage and perforation
K260	K260 Duodenal ulcer, acute with haemorrhage
K262	K262 Duodenal ulcer, acute with both haemorrhage and perforation

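### Objective 4.1 promises to find the most effective alert, but with four algorithms in five Trusts the algorithm cannot be separated from the Trust, and the time series plan has no cross-Trust summary

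*Protocol*

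**What the plan says.** **The promise.** Section 6, objective 4.1, is to "Identify the most effective digital alert for improving outcomes for patients with sepsis". Section 7.4 says this will be done by integrating WorkStreams 1 to 3, with a directed acyclic graph and workshops. It names no estimator.

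**The algorithms.** Table 1 in the first Appendix study assigns NEWS to UCLH, Red Flag to CW and RB, SJSA to ICHT, and a combination to OUHT. A footnote says that the combination is Red Flag plus NEWS2. The background to the second Appendix study adds that workflows and implementation strategies differed, and that the alert arrived with the electronic health record (EHR) everywhere except ICHT.

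**The time series.** Section 10 states "Detailed statistical plans are included in Appendix 1", so the Appendix is the operative plan for WorkStream 2. Its Comparative analysis paragraph says "Each Trust will be modelled separately as the introduction of sepsis alerts and electronic health records is different for each Trust", followed by "Comparisons will be made between the change in slope and step change in counts". No overall estimate is named, although the background to the same study gives its aim as impact across five Trusts. Section 7.2, Secondary analysis, says "We will use a controlled multilevel interrupted time series regression to examine trends in mortality" and does not name the levels.

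**The sixth Trust.** The second Appendix study says "This is a time series analysis across five NHS Trusts in England and one NHS Trust in Wales". Section 7.2, Sampling Strategy, says of that Trust: "In addition, we are working with a Trust in Wales which is still paper based".

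**The concern.** Each algorithm comes bundled with a Trust, a workflow, an implementation strategy and, outside ICHT, a new EHR. If one Trust shows a larger fall in mortality, the data cannot say whether its algorithm or something else in that bundle was responsible. Objective 4.1 would nevertheless turn the difference into a recommendation on which alert to use.

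The separate Trust models add a second gap. They give a set of step and slope changes with no rule for summarising them or for expressing how far they differ. The stated aim, impact across the five Trusts, would then be answered by informal reading of a list. A reader of Section 7.2 and the Appendix together also cannot tell what multilevel refers to.

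**Working it through.** The protocol gives no sample size, power or significance level for the time series, so there is no figure to reproduce. The check is of identifiability, followed by best-case precision.

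**Step 1: can algorithm be estimated alongside Trust?** Build indicator columns from Table 1 (rows UCLH, CW, RB, ICHT, OUHT).

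- Rank of the five Trust indicators: 5.
- Rank of the four algorithm indicators: 4.
- Rank of both sets together: 5.

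Algorithm adds 5 − 5 = 0 estimable parameters once Trust is in the model. The aliasing is complete.

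**Step 2: treat Trust as a random unit.** Take one effect estimate per Trust and four algorithm means. Residual degrees of freedom are 5 − 4 = 1, all of it from the two Red Flag Trusts. The critical value is t(0.975, 1) = 12.71.

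**Step 3: best-case precision.** Let τ be the between-Trust SD of the log effect among Trusts using the same algorithm. The documents do not give τ, so it is assumed over 0.02 to 0.20. Sampling error within Trust is set to zero, which favours the plan. The 95% half-width on the log scale is 12.71 × τ × √2 for two single-Trust algorithms, and 12.71 × τ × √1.5 for Red Flag against a single-Trust algorithm. For τ = 0.05 the first is 12.71 × 0.05 × 1.414 = 0.898, and exp(0.898) = 2.46.

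| τ (assumed) | Single v single, ratio | Red Flag v single, ratio | Single v single if τ were known (1.96) |
|---|---|---|---|
| 0.02 | 1.43 | 1.37 | 1.06 |
| 0.05 | 2.46 | 2.18 | 1.15 |
| 0.10 | 6.03 | 4.74 | 1.32 |
| 0.20 | 36 | 22 | 1.74 |

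For scale, the second Appendix study reports a 23% lower risk of death at ICHT, a ratio of 0.77, or 1/0.77 = 1.30 in the other direction. With τ estimated from these Trusts, every half-width in the table exceeds that entire effect, even at τ = 0.02.

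**Step 4: how far apart would equally effective alerts look?** In a simulation with all four algorithms equally effective and no sampling error, the best-to-worst ratio (from the mean log difference) was 1.10 for τ = 0.05, 1.21 for 0.10 and 1.47 for 0.20. A best alert always appears, whether or not one exists.

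**Step 5: could the OUHT combination help?** If OUHT is modelled as Red Flag plus NEWS with additive effects, the component matrix has rank 3 and leaves 5 − 3 = 2 degrees of freedom. That gains one degree of freedom at the price of an additivity assumption that cannot be tested here.

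**Step 6: what would a summary offer?** A random-effects mean over the five alerting Trusts has 5 − 1 = 4 degrees of freedom. That is limited but usable. The first Appendix study already plans both separate Trust models and a multilevel model clustered on Trust, with a sensitivity check, for process measures. The second study, which carries the mortality outcome, has no counterpart.

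**The case against.** The strongest reply is that separate modelling is reasoned: the interventions differ, each Trust has its own dates, and an average over unlike interventions is not obviously the better target. Objective 2.4 can be answered Trust by Trust. WorkStream 4 is a mixed-methods synthesis and never says it will fit an algorithm regression. The time series adjusts for case mix, the first study compares alerting patients with Suspicion of Sepsis patients, and Section 7.2 plans a comparison by alert type.

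Much of this stands. It supports keeping the Trust-specific models, and it means that baseline and intake differences are partly handled. It does not remove Trust-specific implementation or EHR effects tied to the algorithm. Qualitative evidence can inform a recommendation, but it cannot supply the missing statistical attribution.

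Several stronger readings are tempting and are not supported:

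- *That multilevel and separate models contradict each other.* Section 7.2 also says "All analyses will be adjusted for clustering of patients within wards or Trust sites", so the levels could be wards or sites inside one Trust. The specification is unclear rather than shown to be inconsistent.
- *That separate models waste the staggered go-live dates.* Each model uses its own date.
- *That the Welsh Trust cannot be modelled, or should serve as a never-alerted comparison.* The second study's definition of the intervention also admits a change in screening programme, so a paper-based Trust may have its own interruption.
- *That the set of step and slope tests carries a stated false-positive rate.* The plan sets no significance level for them and no rule based on any one Trust being significant.
- *That national changes in sepsis practice can be separated only by comparing Trusts.* A change dated away from a Trust's go-live can also be modelled within that Trust.

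**Conclusion.** The concern holds in two parts. The first carries the weight: the quantitative design cannot attribute a difference in effect to the algorithm. For NEWS, SJSA and the combination, each in a single Trust, there is no replication at all; for Red Flag it rests on two Trusts. The aliasing follows from Table 1 without any assumption. The interval widths do rest on assumptions: an unknown τ, shown over a range, and zero sampling error. Real intervals would be wider. The t value of 12.71 describes what an algorithm comparison with Trust as the unit would face, not a test that the plan specifies.

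The second part is smaller: no cross-Trust summary is stated for a study whose aim is impact across five Trusts, and the levels of the multilevel model and the interruption for the Welsh Trust are left open. A reader might infer that a pooled effect must become the primary result. The documents do not require that; with unlike interventions it is a trade-off, and a secondary summary is enough.

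**What to change.** 1. Reword objective 4.1, and the matching sentence in Section 7.4, to describe how estimated effects vary between Trust-specific alert packages. State that differences between Trusts will not be attributed to the algorithm.
2. Keep the Trust-specific time series models. Add a random-effects summary of the alerting Trusts' step and slope effects, each Trust with its own date, with a heterogeneity measure and a Hartung-Knapp interval. This parallels the separate-plus-multilevel approach already planned in the first Appendix study.
3. In Section 7.2, Secondary analysis, name the levels of the multilevel time series and align the wording with the Appendix.
4. State what interruption, if any, is modelled for the paper-based Welsh Trust.

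The cost is protocol wording and one second-stage summary of estimates that the plan already produces; no new data are needed. The downside is a wide summary interval from five Trusts and a more modest claim from WorkStream 4.
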